4.2.3 Exploratory Endpoints

N/A

5 Study Enrollment and Withdrawal

Any subject may withdraw from the study at any time. This will not affect the services and care received at the clinic site. If a subject is uncomfortable during the intervention or survey administration, the subject may stop at any time without penalty. If a subject withdraws consent, no further data from that subject will be collected.

5.1 Inclusion Criteria

Dental patients will be eligible for study participation if they meet the following criteria:

- Greater than or equal to 18 years of age.
- Live in any of the 5 boroughs of New York, NY and visit a participating FHC dental clinic for routine dental care.
- Able and willing to provide informed consent, have their oral lesion(s) photograph(s) and accompanying data entered into the Dentrix EHR, and participate in an exit interview.

Dental providers (non-patient subjects) will be eligible for study participation if they meet the following criteria:

- Greater than or equal to 18 years of age.
- Be employed as a dentist or placed as a dental resident at a participating FHC dental clinic.
- Able and willing to provide informed consent and participate in feasibility testing (provider survey or semi-structured interview).

5.2 Exclusion Criteria

Dental patients will be excluded from study participation if they meet the following criteria:

- Have an acute or terminal illness or a serious mental illness or any other severe health condition(s) that might preclude visiting an oral health care provider.
- Are currently participating in another oral health study.

Dental providers (non-patient subjects) will be excluded from study participation if they meet the following criteria:

- Have an acute or terminal illness or a serious mental illness or any other severe health condition(s) that might preclude them from completing the feasibility testing.

5.3 Vulnerable Subjects

No students will be involved in this research. Dental residents and dental faculty clinical advisors (dentists) will be recruited for this study to determine whether the tele-mentoring component will enhance the ability to detect and identify oral lesions in patients during routine dental visits. The voluntary nature of

CONFIDENTIAL

This material is the property of the NYU School of Medicine and Langone Medical Center. Do not disclose or use except as authorized in writing by the study sponsor

their participation will be principal and without undue influence. All dental providers will be told that they have the right to refuse to participate without any compromise to their positions within the NYU Langone Dental Medicine network.

5.4 Strategies for Recruitment and Retention

Patient subjects will be dental patients who are visiting any of the 6 FHC dental clinics for their regular dental appointments. The dental provider will conduct chairside screening to determine patient eligibility for participation. No undue pressure will be given to patients to participate in the study, which is entirely voluntary.

Non-patient subjects will be dental residents and dental faculty who supervise them at any of the 6 FHC dental clinics. Study staff will meet with potential non-patient subjects during team meetings held in each dental clinic to discuss this study. No undue pressure will be given to dental providers to participate in the study, which is entirely voluntary.

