4.2.2 Secondary Study Endpoints

Acceptability will be assessed using patient exit interviews (PEIs) conducted right after the dental visit is completed.

CONFIDENTIAL

This material is the property of the NYU School of Medicine and Langone Medical Center. Do not disclose or use except as authorized in writing by the study sponsor

Interventional Template Version: 28 APR 2017

Acceptability data collection.

Research staff will conduct a brief exit interview with 5 patients at each of the 6 FHC dental clinics with language interpretation services available regarding the acceptability of the intervention. We developed five statements on patient satisfaction with the intraoral cameras and the overall tele-mentoring intervention that will constitute the PEI. Patients will be asked the extent to which they agree with each statement (e.g., “Dentists should discuss with me ways to prevent and screen for oral cancer.”) (strongly agree, agree, disagree, strongly disagree). The acceptability criterion of the intervention will be that 80% or more of patients rate all five administered acceptability questions as “strongly agree” or “agree.” We will evaluate acceptability as described above for feasibility.

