5.4.1 Use of DataCore/Epic Information for Recruitment Purposes

This study will not utilize EPIC to identify subjects.

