6.2.1 Administration of Procedural Intervention

Dental resident and dentist subjects will administer the study during participating patient routine dental visits.

CONFIDENTIAL

This material is the property of the NYU School of Medicine and Langone Medical Center. Do not disclose or use except as authorized in writing by the study sponsor
Interventional Template Version: 28 APR 2017

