7.3 Study Schedule

7.3.1 Screening

The participating dental provider will conduct chairside screening to determine patient eligibility for participation.

Screening Visit (Day 1)

- Obtain informed consent of potential subject verified by signature on written informed consent for screening form.
- Review medical history to determine eligibility based on inclusion/exclusion criteria.
- Review medications history to determine eligibility based on inclusion/exclusion criteria.

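### No rule says which eligible patients are approached for the 5 places per clinic, and screening is left to providers who are themselves subjects, so the acceptability proportion is open to selection

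*Combined protocol and SAP*

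**What the plan says.** Section 5.4 describes the patient pool: "Patient subjects will be dental patients who are visiting any of the 6 FHC dental clinics for their regular dental appointments". It then assigns screening: "The dental provider will conduct chairside screening to determine patient eligibility for participation". Section 7.3.1 repeats this and makes clear that the screener is a provider in the study: "The participating dental provider will conduct chairside screening to determine patient eligibility for participation".

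The same section 5.4 defines the provider subjects: "Non-patient subjects will be dental residents and dental faculty who supervise them at any of the 6 FHC dental clinics". Section 6.2.1 gives them delivery of the intervention: "Dental resident and dentist subjects will administer the study during participating patient routine dental visits".

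On numbers, section 4.2.2 states: "Research staff will conduct a brief exit interview with 5 patients at each of the 6 FHC dental clinics". Section 5.6 gives the total as 30 patients, and section 4.1 places patient screening in months 6 to 12.

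Willingness is part of eligibility. Section 5.1 sets this criterion, whose last item is the exit interview: "Able and willing to provide informed consent, have their oral lesion(s) photograph(s) and accompanying data entered into the Dentrix EHR, and participate in an exit". Section 5.4.1 adds: "This study will not utilize EPIC to identify subjects".

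The text of sections 5.4, 5.6 and 7.3.1 contains no consecutive, random or session-based order of approach, no screening log, and no count of patients eligible, approached or declining.

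**The concern.** The eligibility criteria say who may enter. They do not say which of the patients who qualify are invited when a clinic has only 5 places. The only person named at that step is a provider who is a subject of the study and delivers the intervention. A provider need not intend any bias for the sample to tilt: in a busy session it is easier to put forward a patient who is relaxed, cooperative or does not need an interpreter.

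Acceptability is the study's only secondary objective. The criterion is that at least 80% of patients agree with all five statements. With one arm and a fixed threshold, no comparator cancels a selection effect. Without a log of those not invited, the analyst cannot estimate or adjust for it. Section 3 ties success of the pilot to scale-up of the programme, so a flattering proportion would have a use beyond the pilot.

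**Working it through.** **The plan's own figure.** 5 patients × 6 clinics = 30, as section 5.6 states. Section 9.1 says no sample size calculation was made, so there is no power figure to reproduce.

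**Inputs from the documents.** n = 30; threshold 80%. There are two readings of the pass rule:
- Section 9 gives only the 80% criterion: 0.80 × 30 = 24, so 24 or more must agree with all five items.
- Section 4.2.2 also says acceptability is evaluated as for feasibility. In section 4.2.1 that means the upper 95% confidence bound must exceed 80%. With the exact (Clopper-Pearson) interval, 19/30 has an upper bound of 80.07%, so 19 or more pass. A Wald interval also gives 19; a Wilson interval gives 20.

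**Assumed inputs.** The true proportion p of eligible patients who would agree with all five items, and w, how many times more likely an agreeing patient is to be entered than a non-agreeing one. The documents give neither.

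**Formulas.** Sampled proportion p_s = w·p / (w·p + 1 − p). Chance of passing = P(X ≥ r), X ~ Binomial(30, p_s), with r = 24 or 19. Clustering by clinic is ignored.

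**Example at p = 0.75.** For w = 2, p_s = 1.50 / (1.50 + 0.25) = 0.857. This is the same as passing over half of the non-agreeing patients: 0.75 / (0.75 + 0.125) = 0.857. Passing over 10% of them is w = 1/0.9 = 1.11, and p_s = 0.75 / (0.75 + 0.225) = 0.769. Passing over 20% is w = 1.25, and p_s = 0.75 / (0.75 + 0.20) = 0.789.

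| w | p_s | P(at least 24/30) | P(at least 19/30) |
|---|---|---|---|
| 1 (no tilt) | 75.0% | 34.8% | 94.9% |
| 1.11 | 76.9% | 44.3% | 97.1% |
| 1.25 | 78.9% | 55.0% | 98.6% |
| 1.5 | 81.8% | 70.3% | 99.6% |
| 2 | 85.7% | 87.4% | 99.9% |

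**Another starting value.** At p = 0.70, the chance of at least 24/30 is 16.0% without tilt, and 32.4%, 48.7% and 73.0% for w = 1.25, 1.5 and 2. Under the 19/30 rule it is 84.1% without tilt and 99.7% for w = 2.

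The bias in the proportion itself (p_s − p) does not depend on the pass rule. At p = 0.75 it runs from about 2 points (w = 1.11) to about 11 points (w = 2).

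**The case against.** The strongest reply is that the plan gives providers the task of determining eligibility, not of choosing the five. A reader might infer that providers may hand-pick patients. The documents do not say so; it is an inference from silence. The workflow figure in section 7.1.1 is not shown in the text available, so a recruitment step there cannot be excluded. This stands, and the point is therefore limited to the absence of a rule in the visible text.

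A reader might also infer that nearly all eligible patients go uninvited. No visit volume or eligible count is given. Section 5.1 also refers to patients' lesion photographs; if that implies a lesion, the pool could be much smaller. That inference is not supported.

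There are safeguards. Research staff conduct the exit interviews, with interpretation available (section 4.2.2), and the investigator explains the study at consent (section 12.3.2). No incentives are budgeted (section 14.3), and no motive to select is documented. The first two safeguards may limit response bias and pressure, but they act after a patient has been put forward. An unintended tilt needs no motive.

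Finally, this is the secondary endpoint of a small pilot, for which convenience sampling is common, and under the upper-bound rule the pass decision barely moves. That limits the consequence for pass or fail. It does not remove the bias in the reported proportion.

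**Conclusion.** The concern holds as a gap in the recruitment rule. Providers who are subjects screen at the chairside, nothing visible fixes who is approached for the 5 places per clinic, and analysis cannot repair a selected single-arm proportion.

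The size is not known. It depends on assumed values of w and p and on which pass rule governs. It would be wrong to read the rise from 35% to 87% as the expected effect. That is one assumed tilt under the 24/30 reading, and it requires half of the would-be negative patients to be passed over before they have experienced the intervention. Milder tilts give 44% to 70%. Under the rule that section 4.2.2 refers to, the largest tilt tabulated adds about 5 points. The primary feasibility checklist is completed by providers, so this illustration does not apply to it. The change is worth making because it is cheap and must be in place before enrolment.

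**What to change.** In sections 5.4 and 7.3.1, state that:

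1. In sessions when research staff are present for exit interviews, consecutive eligible adults on the schedules of participating providers are invited until 5 are enrolled at that clinic.
2. The places at each clinic are divided so that each of the 2 dentists completing the checklist there screens at least 1 patient subject. Section 7.1.1 makes this a condition for completing the checklist; without the division, one provider's schedule could fill the quota.
3. The provider only confirms the listed inclusion and exclusion criteria.
4. The numbers eligible, not invited (with reason), declined and enrolled are logged and reported per clinic.

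The total stays at 30 and no new instrument is needed. The clinic's appointment list could serve for the order of approach, so section 5.4.1 need not change. The cost is the added wording, a short log, and possibly slightly slower recruitment. Selection by willingness to take part remains, because section 5.1 makes it an inclusion criterion. The report should acknowledge this and show the refusals.

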5.4.1 Use of DataCore/Epic Information for Recruitment Purposes

This study will not utilize EPIC to identify subjects.

5.5 Duration of Study Participation

The duration of study participation for patient subjects will be from 1-2 days, including follow-up.

The duration of study participation for non-patient subjects will be from 3-6 months.

5.6 Total Number of Subjects and Sites

All subjects will be recruited at the 6 FHC dental clinics in Brooklyn, NY.

The number of patient subjects will total 30 (5 from each of 6 FHC dental clinics).

The number of non-patient subjects will total 18: 12 dental resident and dentist subjects who will complete provider surveys (feasibility checklists), and 6 dental resident subjects who will complete semi-structured interviews.

5.7 Subject Withdrawal or Termination

5.7.1 Reasons for Withdrawal or Termination

Subjects are free to withdraw from participation in the study at any time upon request. An investigator may terminate participation in the study if:

- Any clinical adverse event (AE), laboratory abnormality, or other medical condition or situation occurs such that continued participation in the study would not be in the best interest of the subject
- The subject meets an exclusion criterion (either newly developed or not previously recognized) that precludes further study participation
- Patients will have the right to refuse to participate without any compromise of their health or dental services
- Non-patient subjects will have the right to refuse to participate without any compromise of their employment or standing in the NYU Langone Dental Medicine network

CONFIDENTIAL

This material is the property of the NYU School of Medicine and Langone Medical Center. Do not disclose or use except as authorized in writing by the study sponsor
Interventional Template Version: 28 APR 2017

- If a subject is uncomfortable during an interview or survey administration, s/he may stop at any time without penalty

5.7.2 Handling of Subject Withdrawals or Termination

If a subject withdraws consent, no further data from that subject will be entered into the REDCap database for that subject. Depending on the nature of the request to withdraw, it may be necessary to remove existing data for that subject from the REDCap database.

5.8 Premature Termination or Suspension of Study

This study may be temporarily suspended or prematurely terminated if there is sufficient reasonable cause. Written notification, documenting the reason for study suspension or termination, will be provided by the suspending or terminating party to [name] (PI), HRSA, and regulatory authorities. If the study is prematurely terminated or suspended, the PI will promptly inform the IRB and will provide the reason(s) for the termination or suspension.

Circumstances that may warrant termination or suspension include, but are not limited to:

- Determination of unexpected, significant, or unacceptable risk to subjects
- Demonstration of efficacy that would warrant stopping
- Insufficient compliance to protocol requirements
- Data that are not sufficiently complete and/or evaluable
- Determination of futility

Study may resume once concerns about safety, protocol compliance, data quality are addressed and satisfy the sponsor, IRB, and/or FDA.

6 Study Agent (Study drug, device, biologic, vaccine etc.) and/or Procedural Intervention

The SOPROCARE is intended for clinical practice of general dentistry, as an aid in the diagnosis of pit and fissure caries, as an aid to highlight dental plaque and gingival inflammations (restricted to gingival inflammations which lead to bleeding upon probing) and as intra-oral camera to visualize anatomical details that are invisible to the naked eye or with a mirror (thanks to its magnification). In CARIO mode, the camera helps the dental practitioner to highlight carious warning on pits and fissures of the occlusal side of the teeth. In DAYLIGHT mode, the camera enables you to visualize anatomical details invisible to the naked eye or with a mirror (thanks to its magnification). In PERIO mode, the camera helps the dental practitioner to see the presence of dental plaque but also to highlight gingival inflammations (restricted to gingival inflammations which lead to bleeding upon probing). This mode offers to the dentist and/or hygienist a tool for an improved communication, motivation and education of his/her patients, who will then become aware of their oral health condition.

MORE INVENTIVE. PATENTED AUTOFLUORESCENCE TECHNOLOGY.

The ACTEON® imaging team has patented a technology based on the principle of autofluorescence. ACTEON® intraoral cameras provide a real-time fluorescence signal of the tooth superimposed on its anatomical image, revealing invisible tissues.

SELECTIVE CHROMATIC AMPLIFICATION.

Due to the combination of blue light absorption by soft tissue and selective chromatic amplification, SOPROCARE® improves visibility of all areas of tissue inflammation.

CONFIDENTIAL

This material is the property of the NYU School of Medicine and Langone Medical Center. Do not disclose or use except as authorized in writing by the study sponsor
Interventional Template Version: 28 APR 2017

6.1 Study Agent(s) and Control Description

Prescription Use (Rx): Yes.

LESS INVASIVE. HIGHLIGHT PATHOLOGIES AND MOTIVATE PATIENTS.

The autofluorescence makes it possible to detect decay even at its earliest stages, without subjecting the patient to any unnecessary radiation. SOPROCARE® also reveals dental plaque without using plaque disclosing solutions, and highlights gingival inflammation painlessly.

Improve clinical performance and easily communicate the treatment plan to your patient. The patient is involved in making decisions and accept the treatment.

Images can be captured and stored into any imaging software, giving you all of the necessary tools to practice minimally invasive dentistry.

6.1.1 Acquisition

Commercially via vendor

6.1.2 Device Specific Considerations

Aceton Soprocare Intraoral Camera
Catalog Number: S_950_0002

6.1.3 Procedures for Training Interventionalists and Monitoring Intervention Fidelity

[name] will train and supervise the dental providers, who will administer the intervention.

6.1.4 Assessment of Subject Compliance with Study Intervention

N/A

6.2 Study Procedural Intervention(s) Description

The tele-mentoring intervention involves training dental faculty members and residents to use intraoral cameras to take photographs of oral lesions and place them in the Dentrix electronic health record (EHR), along with descriptions of the lesions. This information will then be sent via Dentrix EHR to [name], the Director of Oral Pathology at NYU Langone Hospital – Brooklyn, and an initial dummy code entry will be placed in the Dentrix EHR. For each patient with a detected lesion, [name] will then review the Dentrix EHR chart and the uploaded photograph(s) of the lesion(s) found and place his observations in the Dentrix EHR. Next, [name] will discuss his findings with the involved dental faculty member / dental resident via secure NYU Langone Health e-mail. The dental provider will then enter an apt comment in the Dentrix EHR, using the following template: “Reviewed entry and contacted patient. Follow-up appointment needed / not needed (+ date) for an appointment on (date).” A second dummy code entry will then be placed in the patient chart in the Dentrix EHR. Once a week, [name] will receive a Dentrix EHR report with the 2 affiliated dummy codes for the tele-mentoring pilot study, and assure that entries for both codes are entered, and the loop is closed.

6.2.1 Administration of Procedural Intervention

Dental resident and dentist subjects will administer the study during participating patient routine dental visits.

CONFIDENTIAL

This material is the property of the NYU School of Medicine and Langone Medical Center. Do not disclose or use except as authorized in writing by the study sponsor
Interventional Template Version: 28 APR 2017

6.2.2 Procedures for Training of Clinicians on Procedural Intervention

[name] will train all dental provider subjects on the use of intraoral cameras and the tele-mentoring procedure. [name] will train all dental resident and dentist subjects in the identification of oral lesions.

6.2.3 Assessment of Clinician and/or Participant Compliance with Study Procedural Intervention

N/A

7 Study Procedures and Schedule

7.1 Study Procedures/Evaluations

7.1.1 Study Specific Procedures

The protocol for the tele-mentoring study was designed by Drs. [name] and [name], and is provided on the following page. This workflow will be refined based upon the results of the planned feasibility and acceptability testing. All study activities will take place in the 6 FHC dental clinics and private offices of NYU Langone Dental Medicine in Brooklyn, NY. The PEIs with patient subjects and the feasibility checklists with provider subjects will take 10-15 minutes to complete. The semi-structured interviews with dental resident subjects will take 30-45 minutes to complete, and will be digitally recorded and transcribed. The transcriptions will be stored in a secure REDCap database. The digital files will be deleted once they are transcribed. No identifying information will be recorded.

A2. Data Collection

[figure not shown]
Feasibility of the integrated intervention will be assessed through dental provider surveys and semi-structured interviews. The dental provider survey, which consists of a checklist of 10 key components of the tele-mentoring intervention to be implemented, will be completed by 2 dentists at each of the 6 FHC dental clinics (n=12) after screening at least 1 patient subject for oral cancer using an intraoral camera, as per the tele-mentoring protocol. Furthermore, after we have reached our target of 30 patient participants (5 patient participants at each of the 6 FHC dental sites), we will engage 6 dental residents (1 at each of the 6 FHC dental clinics) in a semi-structured interview to assess specific barriers they have encountered to sustaining the intervention and strategies for addressing those barriers to facilitate integration of the tele-mentoring intervention into the routine workflow of the dental clinics.

Acceptability of the integrated intervention will be assessed through brief patient exit surveys. Consented participants will be asked to complete a brief patient exit survey at the end of their dental appointments after being screening for oral cancer lesions using an intraoral camera.

The protocol for the tele-mentoring study is provided below:

CONFIDENTIAL

This material is the property of the NYU School of Medicine and Langone Medical Center. Do not disclose or use except as authorized in writing by the study sponsor
Interventional Template Version: 28 APR 2017

